### 1.9.3 Vital signs

All the summaries of vital signs will only include data during treatment period, which are defined as those lab assessments within last dose plus 84 days or last visit of follow up period which comes earlier.

All the listings of vital signs will include all records with an on-treatment flag, i.e., a yes-or-no flag indicating whether the record occurred within last dose plus 84 days.

Analysis in vital sign measurement using descriptive summary statistics for the change from baseline for each post-baseline visit will be performed by vital sign and treatment group.

Change from baseline will only be summarized for subjects with both baseline and post-baseline values and will be calculated as:

$$\text{change from baseline} = \text{post-baseline value} - \text{baseline value}$$

The number and percentage of subjects with newly occurring notable vital signs will be presented. Clinically notable vital sign results are provided in [Table 1-20](#) below. The crude incidence for the treatment period will be shown for entire treatment period.

**Table 1-20 Criteria for notable vital sign abnormalities**

| Vital sign (unit)               | Notable abnormalities          |
|---------------------------------|--------------------------------|
| Systolic blood pressure (mmHg)  | $\geq 140$ mmHg or $< 90$ mmHg |
| Diastolic blood pressure (mmHg) | $\geq 90$ mmHg or $< 60$ mmHg  |
| Pulse (bpm)                     | $> 100$ bpm or $< 60$ bpm      |

#### **1.9.4    Electrocardiogram (ECG)**

All the summaries of ECG will only include data during treatment period, which are defined as those lab assessments within last dose plus 84 days or last visit of follow up period which comes earlier.

All the listings of ECG will include all records with an on-treatment flag, i.e., a yes-or-no flag indicating whether the record occurred within last dose plus 84 days.

The following quantitative variables will be summarized: ventricular rate, RR interval, PR interval, QRS duration, QT interval, and corrected QT interval (QTc). Both Bazett (QTcB) and Fridericia (QTcF) corrections will be presented for QTc.

QTc will be summarized by computing the number and percentage of subjects with:

- $QTc > 500$  msec
- $QTc > 480$  msec
- $QTc > 450$  msec
- QTc changes from baseline  $> 30$  msec
- QTc changes from baseline  $> 60$  msec
- Sinus pause  $> 3$  sec, if appropriate
- PR  $> 250$  msec

Summary statistics will be presented for ECG variables by analysis visit and treatment group.

In addition, shift tables comparing baseline ECG results (normal, abnormal, not available, total) with the maximum on-study result (normal, abnormal, not available, total) will be provided.

A listing of all newly occurring or worsening abnormalities will be provided, as well as a by-subject listing of all quantitative ECG parameters.

#### **1.9.5    Immunogenicity**

A listing of immunogenicity data will be provided.

## **1.10 Sample size calculation**

Not applicable.

## **1.11 Power for analysis of key secondary variables**

Not applicable.

## **1.12 Interim analyses**

Four interim analyses have been done, first one at the time of 120 days safety update; second one for 3 years IA; third one for 4 years IA; and one for 5 years IA.

## 2 Clinical Study Report - Appendix 16.1.9 Documentation of statistical methods

Summary statistics for continuous variables will include N, mean, standard deviation, minimum, lower quartile, median, upper quartile, maximum.

Summary statistics for discrete variables will be presented in contingency tables and will include absolute and relative frequencies.

### 2.1 Analysis of continuous data

Summary statistics (including N, mean, standard deviation, minimum, lower quartile, median, upper quartile, maximum) will be provided for continuous data by visit and treatment group. For PASI score, DLQI total score, HAQ-DI summary statistics will be derived for absolute and percentage changes from baseline.

### 2.2 Analysis of binary (and categorical) data

#### 2.2.1 Summary statistics for binary and categorical data

Summary statistics for discrete variables will be presented in contingency tables and will include absolute and relative frequencies. If applicable, confidence intervals will be derived as well based on the score method including continuity correction [Newcombe 1998]:

With  $z$  as (1-alpha/2)-quantile of the standard normal distribution (SAS:  $z=PROBIT(1-\alpha/2)$ ),  $n$  as total number of subjects (i.e. number of subjects in the denominator), and  $p$  as estimated crude incidence (number of subjects with event /  $n$ ) it is  $q=1-p$

Then the lower limit is for  $p > 0$ , ( $L = 0$  for  $p = 0$ ),

$$L = \max \left( 0, \frac{2np + z^2 - 1 - z\sqrt{z^2 + 2 - \frac{1}{n} + 4p(nq + 1)}}{2(n + z^2)} \right)$$

and the upper limit is for  $p < 1$ , ( $U = 1$  for  $p = 1$ ),

$$U = \min \left( 1, \frac{2np + z^2 + 1 + z\sqrt{z^2 + 2 - \frac{1}{n} + 4p(nq - 1)}}{2(n + z^2)} \right).$$

For time courses of response variables, the point estimate at each time point including 95% confidence interval will be plotted.

#### 2.2.2 Multiple imputations for response variables

In the multiple imputations analysis the response status will be imputed based on the individual treatment arm information.

In case of higher drop-out rates or higher study treatment discontinuations for reasons other than lack of efficacy additional sensitivity analyses will be performed.

Multiple imputation (MI) is a simulation based approach where missing values are replaced by multiple Bayesian draws from the conditional distribution of missing data given the observed data and covariates, creating multiple completed data sets. These completed data sets can then be analyzed using standard methods. [Rubin \(1987\)](#) presented rules how to combine the multiple sets of estimates to produce overall estimates and confidence intervals that adequately incorporate missing data uncertainty.

Missing values for the ‘change from baseline PASI score’ and ‘IGA mod 2011 score’ will be imputed simultaneously based on an underlying joint normal distribution and using a Markov Chain Monte Carlo (MCMC) method. The change from baseline in PASI score appears to follow closer to a normal distribution than the actual PASI score. Assuming normality for the ‘IGA mod 2011 score’ is motivated by [Schaefer \(1997\)](#), where it was shown that the multivariate normal approximation for the imputation of incomplete categorical and binary data is robust.

The imputations will be done separately for each treatment group including baseline weight, failure to at least one previous biologic (yes/no), and number of previous systemic therapies as additional covariates.

The number of imputations will be set to 100, the seed for the random function will be set to 4572304 for this study. To generate the multiple imputed data sets, the SAS procedure MI can be used as follows:

The input data set <pasi\_in> should have one record per subject with baseline PASI score and IGA mod 2011 score as well as all changes from baseline PASI and post-baseline IGA mod 2011 score.

```
ODS LISTING CLOSE;
ODS OUTPUT MissPattern=msgpat VarianceInfo=varinfo ParameterEstimates=param;
PROC MI DATA=<pasi_in> OUT=<impdata> SEED=457<studycode> NIMPUTE=100;
  VAR <baseline weight> <failure to at least one biologic>
      <number of previous systemic therapies>
      <baseline PASI>
      <change from baseline PASI week 1> - <change from baseline PASI week primary endpoint>;
  BY <treatment group>;
RUN;
ODS LISTING;
```

Programming notes:

- The SAS procedure MIANALYZE expects a variable called “\_IMPUTATION\_” which is generated by the MI procedure. It might be needed to set the SAS option “VALIDVARNAME=UPCASE” temporarily in the program before the MI call, this option should be reset after the MIANALYZE call to VALIDVARNAME=V6.
- In case there are no missings in one treatment group, the MI procedure does not impute any values. In this case the corresponding data need to be imputed manually outside PROC MI and added to the dataset <impdata>.

The imputed data are saved in data set <impdata>. The outcomes of interest, i.e. the PASI 50/75/90/100 response and IGA mod 2011 0 or 1 response will be calculated, e.g. as follows:

```
DATA <impdata2>;
  SET <impdata>;
  IF <change from baseline PASI week primary endpoint>/<baseline PASI>=0.90 THEN <PASI 90 response> =1;
  ELSE <PASI 90 response>=0;
  <...repeat for all PASI response...>

  IF <baseline IGA> >=3 THEN DO;
    IF <IGA week primary endpoint> < 1.5 THEN <IGA 0/1 response> =1;
    ELSE IF <IGA week primary endpoint> >=1.5 THEN <IGA 0/1 response> =0;
    ELSE PUT "E" "RROR:" stysid1a=;
  END;
  ELSE IF <baseline IGA>=2 THEN DO;
    IF <IGA week primary endpoint> < 0.5 THEN <IGA 0/1 response> =1;
    ELSE IF <IGA week primary endpoint> >=0.5 THEN <IGA 0/1 response> =0;
    ELSE PUT "E" "RROR:" stysid1a=;
  END;
  ELSE <IGA 0/1 response> =0;
RUN;
```

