### 1.8.1.1 Definition of PASI and related variables

The total BSA affected by plaque-type psoriasis was estimated from the percentages of areas affected, including head, trunk, upper limbs and lower limbs (see below for PASI assessment). The following calculations were done: each reported percentage was multiplied by its respective body region corresponding factor (head = 0.1, trunk = 0.3, upper limbs = 0.2, lower limbs = 0.4). The resulting 4 percentages will be added up to estimate the total BSA affected by plaque-type psoriasis. The PASI scoring system is further described in [Table 1-11](#).

A PASI score ([Fredriksson and Pettersson 1978, Weisman et al 2003, Gottlieb et al 2005](#)) was derived as indicated in [Table 1-11](#). The head, trunk, upper limbs and lower limbs are assessed separately for erythema, thickening (plaque elevation, induration), and scaling (desquamation). The average degree of severity of each sign in each of the four body regions is assigned a score of 0-4. The area covered by lesions on each body region is estimated as a percentage of the total area of that particular body region. Further practical details help the assessment:

1. The neck is assessed as part of the head.
2. The axillae and groin are assessed as part of the trunk.
3. The buttocks are assessed as part of the lower limbs.
4. When scoring the severity of erythema, scales should not be removed.

Because the head and neck, upper limbs, trunk and lower limbs correspond to approximately 10%, 20%, 30% and 40% of the body surface area, respectively, the PASI score was calculated using the formula:

$$\text{PASI} = 0.1 (E_h + I_h + D_h)A_h + 0.2 (E_u + I_u + D_u)A_u + 0.3 (E_t + I_t + D_t)A_t + 0.4 (E_l + I_l + D_l)A_l$$

where E, I, D, and A denote erythema, induration, desquamation, and area, respectively, and h, u, t, and l denote head, upper extremities, trunk, and lower extremities, respectively (see [Table 1-11](#)).

PASI scores can range from a lower value of 0, corresponding to no signs of psoriasis, up to a theoretic maximum of 72.0.

The investigator was only responsible for collecting the components or scoring signs and total regional area. PASI calculations were done via the PASI Score eCRF.

The PASI scores calculated via the PASI Score eCRF will be used in the analysis and for derivation of PASI response values, relapse and rebound (see below).

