### **1.8.4 Handling of missing values/censoring/discontinuations**

As observed value (Follow-up assessment excluded) will be reported primarily for both efficacy and PROs.

Response variables based on PASI score and IGA mod 2011 categories will be imputed with multiple imputation (MI) (Follow-up assessment excluded) as secondary analysis method. Summary tables for PASI scores and IGA mod 2011 categories will also be imputed using MI. Other response variables (e.g. DLQI 0 or 1 achievement) will be imputed with LOCF (Follow-up assessment excluded).

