#### **1.8.4.1 Multiple imputations for response**

The number of imputations will be set to 100 the seed for the random function will be set to 4572304 for this study.

Multiple imputation (MI) is a simulation based approach where missing values are replaced by multiple Bayesian draws from the conditional distribution of missing data given the observed data and covariates, creating multiple completed data sets. These completed data sets can then be analyzed using standard methods. Within this analysis the PASI score change from baseline or IGA mod 2011 categories will be imputed separately and response variables will be derived based on the imputed scores. In the multiple imputation analysis the response status will be imputed based on the individual treatment arm information.

Of note: subjects with missing baseline or subjects with all post-baseline missing will be included in the multiple imputation analysis.

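### The SAP specifies three incompatible multiple-imputation models for PASI and IGA; the joint one cannot be estimated in small groups, and its normal draws can distort PASI 90 and PASI 100

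*SAP*

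**What the plan says.** As-observed results are primary for efficacy, and multiple imputation (MI) is the secondary method (SAP 1.1.1 and 1.8.4). SAP 1.1.1 drops the protocol's non-responder imputation for maintenance of response. MI also feeds the by-visit tables: "Summary tables for PASI scores and IGA mod 2011 categories will also be imputed using MI".

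The imputation model is described three times.

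- **SAP 1.8.4.1, text:** "PASI score change from baseline or IGA mod 2011 categories will be imputed separately".
- **SAP 2.2.2, text:** the two scores "will be imputed simultaneously based on an underlying joint normal distribution and using a Markov Chain Monte Carlo (MCMC) method". Also, "The imputations will be done separately for each treatment group including baseline weight", together with previous biologic failure and number of previous systemic therapies.
- **SAP 2.2.2, sample code:** the input data set is to hold baseline PASI and IGA "as well as all changes from baseline PASI and post-baseline IGA mod 2011 score". The `VAR` list names only the three covariates, baseline PASI and the PASI changes. The next data step nevertheless derives IGA 0 or 1 response from the imputed data set.

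The last visit in the code is a placeholder for a primary-endpoint week, but this extension has no primary efficacy endpoint. The `BY` variable is a placeholder for treatment group. SAP Table 1-2 lists eight efficacy groups split by switch at Week 156, against five arms on entry. No bound or rounding is given for the draws, although "PASI scores can range from a lower value of 0, corresponding to no signs of psoriasis", and PASI 100 is defined as a score of 0.

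**The concern.** Two programmers following this SAP could produce different MI results without either departing from it. With non-responder imputation dropped, MI is the only general adjustment for dropout in PASI and IGA response, so the choice of model matters.

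Two technical questions follow. The first is whether the joint model can be estimated at all, since it treats every visit's PASI and IGA as separate variables within each group. The second is whether normal draws suit PASI change. Many subjects on an effective drug sit at or near complete clearing, and a normal distribution has no such boundary. At stake are the MI versions of PASI 90 and PASI 100 response, and possibly visible negative PASI values in the summary tables.

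**Working it through.** **1. Group sizes.** The plan states no figure for the imputation model. Its nearest figure is 148 subjects per group (Protocol 9.7), which reproduces: 918/4 × 0.95 × 0.85 × 0.80 = 148.3. Actual enrolment was 675 (Protocol 3.1): 675/5 = 135 per arm on entry, and 675/8 = 84.4 per group in SAP Table 1-2. Actual group sizes are not in the documents.

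**2. Visits (SAP Table 1-8).** Weeks 1-4 give 4, and Weeks 8-156 every four weeks give 38, so 42 to Week 156. The fixed-interval and switch schedule adds 8, giving 50 to Week 260. The continuing start-of-relapse (SoR) schedule adds 26, giving 68.

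**3. Variables in the model.** PASI-only code: visits + baseline PASI + 3 covariates. Joint model: PASI visits + IGA visits + 2 baselines + 3 covariates.

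| Last visit, schedule | PASI-only code | Joint model |
|---|---|---|
| Week 156 | 42 + 4 = 46 | 84 + 5 = 89 |
| Week 260, fixed interval or switch | 50 + 4 = 54 | 100 + 5 = 105 |
| Week 260, SoR | 68 + 4 = 72 | 68 + 50 + 5 = 123, or 68 + 68 + 5 = 141 with IGA at every visit |

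The 105-variable model has 105 × 106/2 = 5,565 covariance terms.

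**4. Can it be fitted?** A covariance matrix from n subjects has rank at most n − 1. Without an informative or ridge prior (none is specified), p variables need n − 1 ≥ p.

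- n = 148: every version passes.
- n = 135: all pass except p = 141.
- n = 84: p = 46, 54 and 72 pass; p = 89 and above are singular.

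With eight groups averaging 84.4, at least one group has 84 or fewer subjects, so the joint model to Week 260 must be singular there. The PASI-only code needs at least 47, 55 or 73 subjects respectively.

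**5. Normal draws.** The documents give no response rates for this purpose, so the following is simulation on assumed rates: 135 subjects, 8 visits, skewed PASI with a point mass at 0, dropout depending on the previous PASI, 60 replicates of 15 imputations. PASI 100 was counted as change at or above baseline.

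| Assumed PASI 75/90/100 (%) | Missing at last visit | Imputed PASI below 0 | PASI 90 error, overall (among imputed) | PASI 100 error, overall (among imputed) |
|---|---|---|---|---|
| 85/65/35 | 12.5% | 21.6% | −1.5 (−12.6) | −1.0 (−8.1) |
| 85/65/35 | 24.1% | 21.4% | −3.1 (−13.0) | −2.0 (−8.2) |
| 70/45/20 | 13.6% | 14.3% | −0.9 (−7.1) | −0.1 (−0.3) |
| 70/45/20 | 27.8% | 14.8% | −1.7 (−5.8) | 0.0 (+0.2) |
| 85/65/5 | 12.6% | 18.2% | −2.1 (−16.5) | +1.6 (+12.8) |
| 85/65/5 | 25.3% | 17.5% | −4.3 (−17.0) | +3.1 (+12.2) |

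Errors are in percentage points. Over all the settings tried, including others than these, about 5-25% of imputed values were negative. Among imputed subjects, PASI 90 ranged from 17 points low to 2 points high, and PASI 100 from about 19 points low to 13 points high.

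**6. Mechanism.** Take a baseline of 20 and a drawn improvement of 22: PASI is −2 and the ratio is 1.10. Clipping to 0 makes the ratio 1.00. Both meet the 0.90 and 1.00 thresholds, so clipping changes no response. The error comes from the normal shape. Under the literal rule PASI = 0, almost no continuous draw would count as PASI 100.

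**7. Choice of scale for the fix.** A cleared donor with baseline 30 has an absolute change of 30. Given to a recipient with baseline 20, that makes PASI −10; with baseline 40, it makes PASI 10, which is not clear. On the percent scale the donated value is 100% in both cases. In simulation, matching on absolute change gave PASI 100 of 23% against a true 43%, while matching on percent improvement removed the bias.

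**The case against.** The strongest reply is that the stakes are limited and the SAP leaves room for a workable reading. MI is secondary, no hypothesis is tested, and the primary objective is safety. The code is offered as an example. The SAP gives reasons for normality: change is closer to normal than the score, and it cites a robustness result for categorical data. SAP 2.2.2 also promises further sensitivity analyses if dropout is higher. All of this stands and limits the weight of the point, but it does not reconcile the three descriptions.

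A reader might infer more than the documents support:

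- **That the MI cannot be fitted.** This needs the joint model together with the switch-split groups. The only model written as code fits at the average group size on either grouping, and the joint model to Week 156 (89 variables) fits at the five-arm average of 135.
- **That negative scores bias PASI 90 and PASI 100.** Step 6 shows that they do not.
- **That PASI 100 is always understated.** The direction changes with the assumed clearance rate.
- **That mean PASI is biased.** This is not shown. In one check the mean among imputed subjects was 1.91 against a true 1.89, and clipping at 0 made it worse (2.21).
- **That MI is the only imputation left.** SAP 1.8.1 keeps non-responder imputation for some Week 92 and Week 144 dosing records without a matching PASI.

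**Conclusion.** The MI specification is internally contradictory and incomplete. That finding is documentary and rests on no assumption: there are three models, an undefined end week and undefined groups.

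That the joint version is inestimable is conditional. It holds in any group no larger than the number of variables. It must occur in at least one group if the eight switch-split groups are used to Week 260, given a non-informative prior.

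That unbounded normal draws can give PASI below 0 follows from the model. The 5-25% frequency and the distortion of PASI 90 and PASI 100 come from simulation on assumed response rates, correlation and missingness. Among the tabulated scenarios, the overall effect was 0.9 to 4.3 points low for PASI 90, and from 2.0 points low to 3.1 points high for PASI 100. The correction is worth making before the final analysis, but the primary as-observed results are untouched.

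**What to change.** State one model, in the same words, in SAP 1.8.4.1 and 2.2.2:

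- Use fully conditional specification with predictive mean matching on percent PASI improvement and on IGA category. Do not match on absolute PASI change, which leaves both the bias and the negative scores.
- For visits to Week 156, impute by assigned arm, with the baseline covariates and the nearest few analysis visits as predictors.
- For later visits, use the same method and short predictor list, and name the post-Week-156 groups. This keeps the planned by-visit MI to Week 260.
- Put IGA into the code, and replace the primary-endpoint placeholder with the actual weeks.
- Keep 100 imputations and the stated seed.

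The cost is SAP wording and reprogramming of one macro. The drawback is that small groups will offer few donors.

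### The example imputation code in SAP 2.2.2 leaves IGA out of the imputation, and its response rule would then score a missing IGA as a response when baseline IGA is 2 or more

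*SAP*

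**What the plan says.** SAP 1.8.4 makes as-observed values the main presentation; they "will be reported primarily for both efficacy and PROs". MI is the secondary method for response based on PASI and on IGA. Section 1.8.4.1 says the PASI change and the IGA categories are imputed separately, with response derived from the imputed scores. Section 2.2.2 says instead that the two "will be imputed simultaneously based on an underlying joint normal distribution and using a Markov Chain Monte Carlo (MCMC) method".

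Section 2.2.2 then gives example code:

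- The input data set is to hold baseline PASI and IGA "as well as all changes from baseline PASI and post-baseline IGA mod 2011 score".
- The code is introduced with the words "the SAS procedure MI can be used as follows". Its VAR statement names baseline weight, prior biologic failure, the number of earlier systemic therapies, baseline PASI, and finally "<change from baseline PASI week 1> - <change from baseline PASI week primary endpoint>". No IGA variable appears, and no second call is printed.
- "The imputed data are saved in data set <impdata>", and the derivation step reads that data set.
- For baseline IGA of 3 or more the rule is "IF <IGA week primary endpoint> < 1.5 THEN <IGA 0/1 response> =1". For baseline IGA of 2 the cut-off is 0.5. A `>=` test sets the response to 0, and a last branch prints an error.

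**The concern.** The prose and the code describe different analyses. The cut-offs of 1.5 and 0.5 show that the derivation expects imputed IGA values: observed scores are whole numbers from 0 to 4, so fractional cut-offs are needed only for draws from a normal model. Yet the printed call that feeds the derivation does not produce such draws.

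The derivation also fails in the wrong direction. For any non-missing number, the `<` and `>=` tests between them cover every case, so the error branch can only have been meant for missing values. A missing value satisfies the first test, so it becomes a response and nothing is flagged. Subjects who drop out would be counted as successes in the analysis meant to show how sensitive the IGA result is to drop-out. The SAP specifies no other method for missing IGA response: supportive analyses are marked not applicable in 1.8.5, and 2.2.2 mentions only unspecified sensitivity analyses if discontinuation is higher.

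**Working it through.** The plan states no figure to reproduce, so the check is of the code's logic and then of scale.

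**Software behaviour assumed.** The documents name SAS but do not state these two rules, which are standard: a numeric missing compares below every number, and PROC MI leaves variables outside the VAR list unchanged in its output.

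**Step 1: is IGA imputed by the printed call?** SAP 1.8.4, 1.8.4.1 and the prose of 2.2.2 all say IGA is imputed. The printed VAR list holds three covariates, baseline PASI and the PASI changes. IGA is in the input but not in VAR, so it leaves the call as it entered. If imputation is meant to be simultaneous, the VAR list is incomplete. If it is meant to be separate, the IGA call and the step joining its output to the PASI output are not shown.

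**Step 2: what does the rule do?** The printed rule was run for baseline IGA in {missing, 0, 1, 2, 3, 4} crossed with post-baseline IGA in the same set, which is 6 × 6 = 36 cases.

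| Case | Result |
|---|---|
| Both values observed (25 cases) | All agree with the responder definition in SAP 1.8.1.1: score 0 or 1 and at least 2 points better |
| Post-baseline missing, baseline 2, 3 or 4 | Response = 1 |
| Post-baseline missing, baseline 0, 1 or missing | Response = 0 |
| Error branch reached | 0 of 36 |

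With a missing test placed first, exactly 3 of the 36 cases change (post-baseline missing with baseline 2, 3 or 4). All three now reach the error branch, and the 25 complete cases still agree with the definition.

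PASI does not share the fault: a missing PASI change fails the `>=` test and is scored as non-response.

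**Step 3: how large is the effect if IGA is left out?** Let m be the share with missing IGA, p their true response rate and r the observed rate in the rest, all with baseline IGA of 2 or more.

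- Rate from the code: (1 − m)r + m
- True rate: (1 − m)r + mp
- Difference: m − mp = m(1 − p), whatever r is

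The documents give neither m nor p, so a range is shown, in percentage points:

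| m | p = 80% | p = 60% | p = 40% |
|---|---|---|---|
| 10% | +2 | +4 | +6 |
| 16% | +3.2 | +6.4 | +9.6 |
| 20% | +4 | +8 | +12 |
| 30% | +6 | +12 | +18 |

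The 16% row is for scale only. The protocol's Amendment 1 rationale reports about 108 of 675 subjects discontinued, and 108/675 = 16%. That is not the share with missing IGA at any visit.

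The value 1 would be the same in all 100 imputed data sets. It adds no between-imputation variance, so the confidence interval would not widen to show the problem.

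**The case against.** The strongest reply is that the plan itself is sound and only an example is incomplete. Several statements say IGA is imputed, the input data set contains it, 2.2.2 defends a normal model for it, and the fractional cut-offs presuppose it. The code is a template made of placeholders. It refers to a primary-endpoint week although this study's primary variable is safety, so it must be rewritten before it can run. A programmer who follows the prose gets no inflation. The production program may well differ from the printed block.

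All of this is right, and it is why the inflation is stated as conditional. It does not remove the mismatch. The prose cannot settle what the programmer should do while 1.8.4.1 and 2.2.2 name different imputation schemes, and the safeguard in the derivation fails under either scheme if any IGA value is left missing.

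It is also fair that an odd MI result could be noticed beside the as-observed one, although detection is not assured. SAP 1.8.4.1 includes subjects with no post-baseline values in the MI analysis, but that does not by itself show that the derivation must handle missing values: imputation would fill them first, and Table 1-1 excludes such subjects from the full analysis set. The point does not depend on them, because missing visits after drop-out are enough.

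**Conclusion.** The concern holds. From the SAP text alone, the printed imputation omits IGA, the derivation takes IGA response from that imputation's output, and two sections contradict each other on separate or simultaneous imputation. Given the standard SAS rules above, an unimputed IGA is scored as a response for baseline IGA of 2, 3 or 4, and the error check cannot fire.

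The inflation of 2 to 18 points applies only if IGA is left out, and it rests on the assumed ranges for m and p. If IGA is imputed as the prose says, it is zero. The exposure is limited to the secondary MI analysis of IGA 0/1 response. As-observed efficacy, the MI results for PASI and the safety results are unaffected, and SAP 1.8.3 plans no hypothesis test.

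**What to change.** 1. State one scheme in both 1.8.4.1 and 2.2.2. If it is simultaneous, add baseline IGA and every post-baseline IGA score to the VAR list. If it is separate, print the second PROC MI call for IGA and the step that joins its output to the PASI output by subject and imputation number.
2. In the derivation, test for a missing post-baseline IGA before the 1.5 and 0.5 comparisons and send such records to the error message.

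The cost is a few lines of SAP text and code. No new data are needed, and results for complete records do not change.
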